2. STUDY OBJECTIVES

2.1. Primary Objective

The primary objective is to assess the efficacy of etrasimod on clinical remission in Japanese subjects with moderately to severely active UC at timepoints up to 52 weeks of treatment (12 weeks in Study APD334-302 plus 40 weeks in Study APD334-308).

2.2. Secondary Objective

The secondary objective is to assess the efficacy of etrasimod on clinical response, symptomatic response and remission, endoscopic changes, corticosteroid-free remission, and mucosal healing in Japanese subjects with moderately to severely active UC at timepoints up to 52 weeks of treatment (12 weeks in Study APD334-302 plus 40 weeks in Study APD334-308).

2.3. Safety Objective

The safety objective is to assess the long-term safety of etrasimod in Japanese subjects with moderately to severely active UC after daily doses of 2 mg for up to 52 weeks (12 weeks in Study APD334-302 plus 40 weeks in Study APD334-308).

3. INVESTIGATIONAL PLAN

3.1. Summary of Study Design

[figure not shown]
This is a multicenter, double-blind, placebo-controlled extension study of APD334-302 (12-week, randomized, double-blind, placebo-controlled induction study) to evaluate the efficacy and safety of etrasimod 2 mg in Japanese subjects with moderately to severely active UC. The study consists of a 40-Week Treatment Period and a 4-Week Follow-Up Period (Figure 2).

Japanese subjects who completed the Week 12 visit of Study APD334-302 are eligible for this study. The Week 12 visit of Study APD334-302 serves as the Day 1 visit of this study. Subjects will continue with the same blinded treatment assigned in Study APD334-302 for a total treatment duration of 52 weeks (12 weeks in Study APD334-302 plus 40 weeks in Study APD334-308).

Disease worsening will be monitored by Investigators through the treatment period. Subjects who either experience disease worsening or complete all study procedures at Week 52 will have the option to enroll into the APD334-303 OLE study if they meet all eligibility criteria.

Subjects who discontinue from the study and do not participate in the OLE study will have 2-Week and 4-Week Follow-Up visits after the last on-treatment visit/Early Termination visit (Table 7).

Figure 2: Study Design

3.2. Rationale for Study Design

This study is designed to evaluate the efficacy and safety of etrasimod in Japanese subjects with moderately to severely active UC. Subjects may continue existing nonbiologic therapy for UC (eg, 5-ASA, corticosteroids) per the concomitant medication and dose stabilization criteria. As preexisting background therapy is allowed, a placebo comparator is justified.

The duration of study treatment is up to 52 weeks, which includes 12 weeks in Study APD334-302 and 40 weeks in Study APD334-308. This 40-week study will provide subjects with 52 weeks of treatment exposure and enable bridging of efficacy and safety of Japanese subjects to the global population treated in Study APD334-301. The 2-Week and 4-Week Follow-Up visits will provide off-treatment safety information.

The etrasimod dose of 2 mg once daily is based on findings of previous Phase 1 and Phase 2 studies, and in particular data from the Phase 2 APD334-003 placebo-controlled study. In the APD334-003 study, subjects received etrasimod 1 mg, etrasimod 2 mg, or placebo. Subjects in the etrasimod 2 mg group experienced a statistically significant improvement in the primary endpoint, the mean difference from placebo at Week 12 in the adapted Mayo score (least squares mean [standard error] difference: -0.99 [0.42]; p = 0.0091) compared with placebo. The etrasimod 2 mg group also experienced significant improvement in all secondary endpoints compared with the placebo group at Week 12, including improvement in the total Mayo Score (estimated least squares mean [standard error] difference from placebo: -1.27 [0.55]; p = 0.0100), and higher percentage of subjects with endoscopic improvement (41.8%, difference from placebo: 24.4%, p = 0.003).

Treatment-emergent adverse events (TEAEs) in the 1 mg, 2 mg, and placebo groups were reported for 59.6%, 56.0%, and 50.0% of subjects, respectively; treatment-related TEAEs were reported for 7.7%, 10.0%, and 5.6% of subjects, respectively; serious adverse events (SAEs) were reported for 5.8%, 0%, and 11.1% of subjects, respectively; and TEAEs leading to discontinuation of study treatment were reported for 5.8%, 8.0%, and 0% of subjects, respectively. No subjects died during the study. Overall, the 2 mg dose demonstrated a favorable safety profile and was chosen as the dose for the current Phase 3 program.

The primary endpoint of clinical remission at Week 52 as assessed using the modified Mayo Score (MMS) is standard, widely used, and is in accordance with the nonbinding US Food and Drug Administration (FDA) Draft Guidance for Industry *Ulcerative Colitis: Clinical Trials Endpoints* (FDA 2016). Other endpoints for the study are widely used and considered reliable measures of efficacy and safety.

The study is powered to the primary endpoint for demonstrating a statistically significant difference in clinical remission between etrasimod therapy and placebo at Week 52.

Subjects meeting predefined eligibility criteria during the treatment period will be eligible to enter the APD334-303 OLE study (Section 5.1.1) provided they meet all entry criteria.

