The safety objective is to assess the long-term safety of etrasimod in Japanese subjects with moderately to severely active UC after daily doses of 2 mg for up to 52 weeks (12 weeks in Study APD334-302 plus 40 weeks in Study APD334-308).

CCI

Study design:

This is a multicenter, double-blind, placebo-controlled extension study of APD334-302 (12-week, randomized, double-blind, placebo-controlled induction study) to evaluate the efficacy and safety of etrasimod 2 mg in Japanese subjects with moderately to severely active UC. Study APD334-308 consists of a 40-Week Treatment Period and a 4-Week Follow-Up Period.

Japanese subjects who completed the Week 12 visit of Study APD334-302 are eligible for the APD334-308 study. The Week 12 visit of Study APD334-302 serves as the Day 1 visit of Study APD334-308. Subjects will continue with the same blinded treatment assigned in Study APD334-302 for a total treatment duration of 52 weeks (12 weeks in Study APD334-302 plus 40 weeks in Study APD334-308).

End of 40-Week Double-Blind Treatment Period

Disease worsening will be monitored by Investigators through the Treatment Period. Subjects who either experience disease worsening or complete all study procedures at Week 52 will have the option to enroll into the APD334-303 open-label extension (OLE) study if they meet all eligibility criteria. Subjects may be eligible to enroll in the OLE study provided their endoscopic score (ES) is > 2 and they meet one of the following entry criteria:

- Rectal bleeding (RB) subscore ≥ 2 at 2 timepoints at least 7 days and no more than 14 days apart
- RB + stool frequency (SF) subscore ≥ 4 at 2 timepoints at least 7 days and no more than 14 days apart
- RB subscore \geq 2 or RB + SF subscores \geq 4 (in any order) at 2 timepoints at least 7 days and no more than 14 days apart

For subjects discontinuing prior to Week 52, an endoscopic evaluation is required to confirm eligibility for the OLE study. An endoscopy should be performed upon the appearance of UC symptoms but no more than 14 days after the second timepoint for entry criteria above.

A proctosigmoidoscopy does not need to be repeated if performed within the last 4 weeks. Subjects who do not participate in the OLE study will have 2-Week and 4-Week Follow-Up visits after their last on treatment visit/Early Termination visit.

Number of subjects (planned):

Approximately 35 Japanese subjects are planned to be enrolled into this study.

Eligibility criteria:

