6. STUDY TREATMENTS

6.1. Treatments Administered

During Study APD334-302, subjects were randomly assigned to 1 of 2 treatment groups (etrasimod or placebo) in a 2:1 ratio. Subjects will continue their treatment assignments during this study. Study treatment is outlined in Table 1.

Table 1: Study Treatment

Study treatment name	Etrasimod	Placebo
Dosage formulation	2 mg tablet	Matching tablet
Unit dose strength/dosage level	1 tablet once daily	1 tablet once daily
Route of administration	By mouth	By mouth
Packaging and labeling	Study treatment will be provided in 40-cc, induction-sealed, high-density polyethylene bottles with child-resistant screw caps. Each bottle will be labeled as required per country requirement. These bottles should be stored at 15 to 25°C (59 to 77°F).	Study treatment will be provided in 40-cc, induction-sealed, high-density polyethylene bottles with child-resistant screw caps. Each bottle will be labeled as required per country requirement. These bottles should be stored at 15 to 25°C (59 to 77°F).

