10.2. Determination of Sample Size

Approximately 35 Japanese subjects in the parent Study APD334-302, and those subjects may be eligible to enroll in Study APD334-308.

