10.12. Testing Strategy

10.12.1. Efficacy Analysis

The primary analysis of the proportion-based efficacy endpoints will be carried out using the Cochran-Mantel-Haenszel (CMH) method, stratified by (a) naive to biologic or JAK inhibitor therapy at APD334-302 study entry (yes or no), (b) baseline corticosteroid use (yes or no), and (c) baseline disease activity (MMS: 4 to 6 or 7 to 9). Results will be expressed as the number of subjects in remission, remission percentages, difference in remission percentages, odds ratio, and associated 95% confidence intervals (CIs).

Due to the limited number of subjects anticipated to enroll in this study, there will be no hypothesis testing on any efficacy endpoint. Inferential statistics will be limited to 95% CIs.

Full details of the efficacy analysis will be documented prior to database lock in the SAP.

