6.5. Statistical Tests

Due to the limited number of subjects anticipated to enroll in this study and central randomization not designed to control for allocation ratio in Japan. Point estimate with 95% confidence intervals (CIs) and nominal p-values (2-sided) will be reported.

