7. DETERMINATION OF SAMPLE SIZE

There is no formal sample size estimation for Study APD334-308. The number of subjects to be enrolled in this study was determined by number of Japanese subjects enrolled in Study APD334-302, and those subjects were eligible to enroll according to Study APD334-308 protocol.

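### Protocol 3.2 claims power to show a significant Week 52 remission difference, but the protocol plans no hypothesis test and the SAP reports no sample size calculation

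*Protocol*

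**What the plan says.** Protocol 3.2, the design rationale, states: "The study is powered to the primary endpoint for demonstrating a statistically significant difference in clinical remission between etrasimod therapy and placebo" at Week 52. It attaches no power, alpha, assumed remission rate or dropout allowance.

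Other current sections say otherwise:

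- Protocol 10.12.1, giving the limited number of subjects as its reason, says "there will be no hypothesis testing on any efficacy endpoint. Inferential statistics will be limited to 95% CIs".
- Protocol 10.2 gives "Approximately 35 Japanese subjects in the parent Study APD334-302", who may then be eligible for this study. The synopsis says "Approximately 35 Japanese subjects are planned to be enrolled into this study". Neither gives a calculation.
- SAP 7 says "There is no formal sample size estimation for Study APD334-308" and "The number of subjects to be enrolled in this study was determined by number of Japanese subjects enrolled in Study APD334-302".

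On allocation, Protocol 6.1 says subjects were "randomly assigned to 1 of 2 treatment groups (etrasimod or placebo) in a 2:1 ratio" in the parent study. SAP 6.5 adds that this was "central randomization not designed to control for allocation ratio in Japan".

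For the primary endpoint, SAP 16.1.3 reports the difference in remission percentages and the odds ratio, each with a 95% CI, and a nominal p-value from Fisher's exact test.

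**The concern.** A study is powered for a comparison when its size was chosen, or at least checked, so that a specified test detects a specified difference with a specified probability. Here there is no planned efficacy test, no specified difference, and a size set by how many Japanese subjects the parent study enrolled. Section 3.2 therefore states a property the design lacks.

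The stake is interpretation. Protocol 1.3 says the results will support approval in Japan, and the SAP will print a Fisher p-value for the primary endpoint. Read with Section 3.2, a p-value above 0.05 looks like a properly powered comparison that failed. A study of about 35 subjects would often give that result even if the drug works well.

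Two smaller items share the root:

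- The tipping-point analysis in Protocol 10.4 is to display where results change from significant to non-significant, although 10.12.1 plans no test.
- Protocol 10.12.1 confines inference to confidence intervals, yet SAP 6.5, 8.4 and 16.1.3 add nominal p-values. SAP 3.3, which lists changes from the protocol, records the removal of the CMH method but not this addition.

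**Working it through.** **Step 1: the text.** Section 3.2 asserts power for a significant difference. Section 10.12.1 says there is no test and gives small numbers as the reason. SAP 7 says no formal size estimation exists. These cannot all be true. Section 10.2 does not mention power; it is consistent with SAP 7 because its number depends only on enrolment. The plan states no power figure, so there is none to reproduce.

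**Step 2: inputs for an illustration.**

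- From the documents: about 35 subjects, 2:1 allocation (23:12), and Fisher's exact test.
- Assumed: placebo remission of 5, 10, 15 or 20%, true differences of 20, 25 or 30 points, and two-sided alpha of 0.05.
- Because the split in Japan was not controlled and fewer than 35 may enter, 20:10 and 20:15 are also shown.

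**Step 3: exact power.** Power = sum of Bin(x; n_E, p_E) × Bin(y; n_P, p_P) over all outcomes (x, y) with two-sided Fisher p ≤ 0.05. The ranges below run over the four placebo rates.

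| Etrasimod:placebo | +20 points | +25 points | +30 points | Difference for 80% power |
|---|---|---|---|---|
| 23:12 | 0.111-0.138 | 0.221-0.226 | 0.325-0.368 | 46.5-51.0 points |
| 20:10 | 0.065-0.131 | 0.152-0.202 | 0.273-0.300 | 49.5-57.0 points |
| 20:15 | 0.201-0.217 | 0.302-0.361 | 0.419-0.514 | 41.5-47.0 points |

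For splits of 35 from 26:9 to 18:17, power for 20-30 points runs from 0.058 (26:9, +20, placebo 5%) to 0.595 (19:16, +30, placebo 5%).

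**Step 4: chance of a non-significant result when the true difference is 20-30 points.**

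- 23:12: 1 − 0.368 = 0.63 to 1 − 0.111 = 0.89.
- 20:10 to 20:15: 1 − 0.514 = 0.49 to 1 − 0.065 = 0.93.
- Extreme splits of 35: 1 − 0.595 = 0.41 to 1 − 0.058 = 0.94.

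**Step 5: smallest observed difference with p ≤ 0.05, when 0-25% of placebo subjects remit.**

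- 23:12: 8/23 against 0/12, 34.8 points, p = 0.032.
- 20:10: 8/20 against 0/10, 40.0 points, p = 0.029.
- 20:15: 6/20 against 0/15, 30.0 points, p = 0.027.

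**Step 6: less conservative method.** The normal approximation with pooled variance at 23:12 gives 0.232 for 10% vs 30%, 0.331 for 10% vs 35% and 0.444 for 10% vs 40%. Fisher gives 0.130, 0.226 and 0.343. The placebo group size for 80% power at 2:1 is

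m = [1.96 × √(1.5 × p̄(1 − p̄)) + 0.842 × √(p_P(1 − p_P) + p_E(1 − p_E)/2)]² / d², with p̄ = (p_P + 2p_E)/3.

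For 10% vs 30%: p̄ = 0.2333 and m = (1.015 + 0.372)² / 0.04 ≈ 48.1, so 49, and the total is 3 × 49 = 147. The totals for 10% vs 35% and 10% vs 40% are 102 and 75.

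**Step 7: the one responder comparison in the protocol.** Section 3.2 reports Phase 2 endoscopic improvement at Week 12 of 41.8%, which is 24.4 points above placebo, so placebo = 41.8 − 24.4 = 17.4%. Exact power for that pair is 0.209 at 23:12, 0.193 at 20:10 and 0.293 at 20:15. This is a different endpoint and visit and serves only as illustration.

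**The case against.** The best case against acting is that the sections governing the analysis are already right. Protocol 10.12.1, SAP 7, and SAP 6.5 and 8.4 (nominal p-values, no multiplicity adjustment) leave little room to treat the Week 52 comparison as confirmatory. The documents also place the study in a bridging role, with data integrated with the global studies and a separate combined analysis of APD334-302 and APD334-308. On this view the error is one stray rationale sentence. That limits the harm, but it does not make the sentence true, and nothing in the documents gives it another meaning.

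The power figures depend on assumed rates and on the test. The protocol's own method was stratified CMH, and Fisher came with the SAP. The normal approximation gives higher values (Step 6), which still do not approach 80% for differences of 20-30 points. The contradiction uses none of these figures and is textual rather than arithmetical.

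The secondary items are weaker. Protocol 10.4 says sensitivity analyses may be performed, a tipping boundary could be drawn from whether a 95% CI excludes no effect, and the SAP text shown does not take that analysis forward. The unlisted p-values are a separate consistency matter. Neither adds weight to the main point.

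**Conclusion.** The concern holds. Section 3.2 is wrong as written: it is contradicted within the protocol by 10.12.1 and in the SAP by Section 7. That conclusion needs no assumption.

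The gap is large. Under the stated assumptions, the design at its nominal 2:1 split has well under half the usual 80% power for true differences of 20-30 points, and across the 20:10 to 20:15 splits it would need a difference of about 42-57 points to reach 80%. The consequence is confined to how a non-significant result is read and what evidential weight the study claims; no planned SAP analysis or decision rule depends on the sentence. It should be corrected because the study is meant to support approval.

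**What to change.** Replace the sentence in Protocol 3.2 with a statement that the number of subjects follows from Japanese enrolment in Study APD334-302, that the study is not powered for hypothesis testing, and that inference is by point estimates and 95% CIs. In the same edit, reconcile the significance boundary in Protocol 10.4 with 10.12.1, for example by defining it through the confidence interval.

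If the protocol is no longer being amended, which is likely since the SAP is V1.0 of 28 September 2022 and refers to subjects already enrolled, put the same statement in SAP 3.3 and in the clinical study report. That version should add that the Fisher p-values in SAP 6.5, 8.4 and 16.1.3 are nominal and descriptive, and list them as a change from Protocol 10.12.1.

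The cost is either a short protocol amendment or one SAP entry and one study report sentence. Data collection and the planned SAP analyses do not change. The only downside to the sponsor is a less favourable, but accurate, description of the design.

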3.3. Study Duration

The APD334-308 study consists of a 40-Week Treatment Period and a 4-Week Follow-Up Period. The study duration is expected to be approximately 2 years.

The End of Study is the date when the last subject completes his/her last study visit.

3.4. Independent Data Monitoring Committee

An independent Data Monitoring Committee (DMC) will be utilized to monitor the safety of subjects and to enhance the integrity and credibility of the study. The roles and responsibilities of the DMC are described in detail in the DMC Charter.

The DMC will abide by the principles set forth in the FDA Guidance for Industry, *Clinical Trial Sponsors*, *Establishment and Operation of Clinical Trial Data Monitoring Committees* (FDA 2006). As part of its role, the DMC will conduct reviews of accumulating safety and efficacy data at specified intervals during the conduct of the trial, according to the guidelines detailed in the DMC Charter. DMC recommendations to the study team will be communicated in a blinded fashion (ie, treatment assignment for individual subjects will not be shared). To ensure the scientific integrity of the study, members of the DMC will not be directly involved in the ongoing management of the study.

In addition to members of the DMC, an independent statistician responsible for interacting with the DMC will have access to unblinded study data. This statistician will not be directly involved in the conduct of the study.

4. SELECTION OF STUDY POPULATION

The study population consists of men, women and adolescents (hereafter referred to as men and women), 16 to 80 years of age, inclusive, with moderately to severely active UC.

4.1. Inclusion Criteria

Subjects must meet ALL of the following inclusion criteria to be eligible for enrollment into the APD334-308 study:

- 1. Must have completed the Week 12 visit of Study APD334-302
- 2. Ability to provide written informed consent or assent (parent or legal guardian must provide consent for a subject < 20 years of age or as required per local regulations who has assented to participate in the study) and to be compliant with the schedule of protocol assessments. Enrollment of subjects < 20 years should be conducted only if acceptable according to local laws and regulations.
- 3. Eligible women of childbearing potential must fulfill the following:
 - a. Have a negative urine beta-human chorionic gonadotropin (β-hCG) pregnancy test at the Week 12 visit of Study APD334-302
 - b. Not breastfeeding
- 4. Females must meet either a or b of the following criteria and males must meet criterion c to qualify for the study:
 - a. A female who is not of childbearing potential must meet 1 of the following:
 - Postmenopausal, defined as no menses for 12 months without an alternative medical cause
 - Permanent sterilization procedure, such as hysterectomy, bilateral salpingectomy, or bilateral oophorectomy
 - b. Nonpregnant female of childbearing potential must agree to using a highly effective contraception method during treatment and for 30 days following treatment that can achieve a failure rate of less than 1% per year when used consistently and correctly. The following are considered highly effective birth control methods:
 - Combined (estrogen and progestogen containing) oral hormonal contraception associated with inhibition of ovulation
 - Progestogen-only oral hormonal contraception associated with inhibition of ovulation
 - Intrauterine device (IUD)
 - Intrauterine hormone-releasing system
 - Bilateral tubal occlusion
 - Vasectomized partner, provided that partner is the sole sexual partner of the female of childbearing potential trial participant and that the vasectomized partner has received medical assessment of the surgical success

- Sexual abstinence (complete sexual abstinence defined as refraining from
 heterosexual intercourse for the entire period of risk associated with study
 treatments). The reliability of sexual abstinence needs to be evaluated in relation
 to the duration of the clinical study and the preferred and usual lifestyle of the
 subject. Periodic abstinence (calendar, symptothermal, post-ovulation methods) is
 not acceptable.
- c. A male subject with a pregnant or nonpregnant female of childbearing potential partner must agree to using condoms during treatment and for 30 days following treatment

4.2. Exclusion Criteria

Subjects who meet any of the following exclusion criteria will not be eligible for enrollment into the study:

1. If the Investigator considers the subject to be unsuitable for any reason to participate in the study

Exclusions related to general health

- 2. Subjects requiring partial or total colectomy during the APD334-302 study
- 3. Subjects requiring treatment with prohibited concomitant medications as defined in Section 6.7.3

